5.8. PHARMACOKINETIC SET

The Pharmacokinetic Set will include all subjects in the Safety Set with at least 1 quantifiable postdose PK measurement of etrasimod which is not impacted by protocol violations or events with potential to affect the PK concentration.

5.9. COMPLETERS SETS

The Completers Set (Week 16) will consist of all subjects in the FAS who complete Week 16 visit during the Double-Blind Treatment Period. Subjects will be summarized by treatment to which they were randomized. The Completers Set (Week 24) will consist of all subjects in the FAS who complete Week 24 visit during the Double-Blind Treatment Period. Subjects will be summarized by treatment to which they were randomized.

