4.3. Eligibility Criteria for the Extension Treatment Period

Inclusion Criteria:

1. Completion of the Week 24 study visit (including EGD) including subjects who discontinued study treatment due to lack of clinical efficacy and started rescue therapy between Weeks 16 and 24. Rescue therapy must be discontinued on the day etrasimod is initiated in the Extension Treatment Period.
2. Compliance with study procedures during the Double-Blind Treatment Period as assessed by the Investigator
3. No notable safety concerns during the Double-Blind Treatment Period, as determined by the Investigator
4. Willing to comply with all study visits and procedures for the Extension Treatment Period

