6.7.4. Rescue Therapy

Any new medication or procedure used to treat new or worsened EoE symptoms is considered a rescue therapy. Rescue therapy should not be withheld if, in the opinion of the Investigator, failure to use/implement them would compromise the safety of the subject.

Subjects who discontinue between Week 16 and Week 24 due to lack of clinically meaningful efficacy will be provided the option to remain in the study. For these subjects, rescue therapy may be given until the end of the Double-Blind Treatment Period but must be discontinued upon entry in the Extension Treatment Period during which all subjects receive active treatment.

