11.4.2. Sensitivity Analyses

In addition to the primary method for handling missing data and rescue medication/rescue procedure use in the FAS described in Section 11.4.1, the following sensitivity analyses will be performed for primary, secondary, and selected CCI using alternative methods to handle missing data and/or in alternative analysis populations:

- MI usually assumes that the data are missing at random (MAR) but MAR cannot be verified using the observed data. Therefore, the sensitivity of inferences to departures from the MAR assumption will be examined. For the MI analysis of the primary endpoint of percent change from Baseline in esophageal PEC at Week 16 and Week 24, data MAR within each treatment group will be investigated using tipping point analyses method and results will be described using Rubin’s rule [1]
- Percent change in esophageal PEC from Baseline to Week 16 and Week 24 will be analyzed in the modified Full Analysis Set (mFAS), data will be set to missing after rescue medication/rescue procedure uses
- Proportion of subjects with esophageal PEC of < 15 and ≤ 6 eos/hpf at Week 16 and Week 24 will be analyzed in the FAS using PEC imputed by the MI method discussed in Section 11.4.1
- Proportion of subjects with esophageal PEC of < 15 and ≤ 6 eos/hpf at Week 16 and Week 24 will be analyzed in the mFAS using PEC imputed by the MI method discussed in Section 11.4.1
- Observed data analyses in mFAS, regardless of rescue medication/rescue procedure use and without missing data imputation:
 - For longitudinal continuous variables, a linear mixed effects model will be performed and results will be reported by visit.
 - For longitudinal dichotomous measures, logistic regression analysis may be performed by visit
- Completers analyses (also known as complete case) of primary and secondary endpoints for subjects who complete 16 and 24 weeks of study treatment

- Per Protocol Set analyses in subjects who meet the criteria of Per Protocol definition approved prior to database lock

Detailed sensitivity analysis methods will be described in the SAP.

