3.3. CHANGES TO ANALYSIS FROM PROTOCOL

- Not applicable.

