17.1.5. SUPPLEMENTARY ANALYSIS OF PRIMARY EFFICACY VARIABLE(S)

The primary model as described in Section 16.1.3 will be repeated using the Completers Set and Per Protocol Set as

supplementary analyses. Subgroup analyses will also be performed for the primary model.

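### The SAP defines completers by visit attendance and analyses them with imputation, while the protocol specifies a complete-case analysis of completed treatment

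*SAP*

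**What the plan says.** Protocol 11.4.2 lists, among the sensitivity analyses, "Completers analyses (also known as complete case) of primary and secondary endpoints for subjects who complete 16 and 24 weeks of study treatment".

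SAP 5.9 defines two sets. The Week 16 set takes FAS subjects "who complete Week 16 visit during the Double-Blind Treatment Period" and the Week 24 set is "all subjects in the FAS who complete Week 24 visit during the Double-Blind Treatment Period". Neither requires the subject to be on study drug or to have an endpoint value.

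SAP 17.1.5 says that the primary model "will be repeated using the Completers Set and Per Protocol Set" as supplementary analyses. SAP 3.3, on changes from the protocol, reads "Not applicable".

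Two protocol provisions decide who can attend Week 24. Section 6.7.4 covers staying in the study off drug: "Subjects who discontinue between Week 16 and Week 24 due to lack of clinically meaningful efficacy will be provided the option to remain". It also allows rescue until the end of the double-blind period. The first extension criterion in section 4.3 counts among those who complete the Week 24 visit, with its EGD, "subjects who discontinued study treatment due to lack of clinical efficacy and started rescue therapy between Weeks 16 and 24".

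**The concern.** A completers analysis is read as a check on the primary result: what is seen among subjects who took the treatment for the full period and whose outcome was measured. If membership depends only on attendance, and missing outcomes are filled in by the primary analysis's own imputation model, the check loses both properties. It will also lean towards agreement with the primary analysis, because the two share that model. A reader of the study report who sees the label could take the agreement as independent support. The departure from the protocol is not declared, so nothing would alert that reader.

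**Working it through.** No arithmetic decides this point, and the plan gives no figure to reproduce. The check sets the texts side by side.

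**1. The two specifications**

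| Feature | Protocol 11.4.2 | SAP |
|---|---|---|
| Membership | Weeks of treatment completed | Visit completed (5.9) |
| Endpoint observed | Implied by complete-case | Not required (5.9) |
| Free of rescue | Not stated | Not stated (5.9) |
| Imputation | None, implied by complete-case | Primary model repeated (17.1.5) |
| Change declared | – | None (3.3) |

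**2. Who differs at Week 24.** Under protocol 6.7.4 and 4.3, a subject can stop drug for lack of efficacy after Week 16, start rescue, stay in the study and complete the Week 24 visit. That subject is a Week 24 completer under SAP 5.9. The subject has not completed 24 weeks of treatment, so is not a completer under the protocol. These are treatment failures, so the difference between the sets is not random.

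**3. What happens to their Week 24 PEC.** SAP 17.1.2 sets PEC after rescue to missing and imputes it. SAP Appendix 4 says that therapy begun on or after the last study treatment administration does not count as rescue. These subjects stop drug and then start rescue, so on that reading their PEC stays in as observed. Appendix 4 ties the exception to the follow-up period. For a subject who restarts drug in the extension, it does not say which last administration applies. Both readings are open, and neither gives an analysis of completed treatment.

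**4. Who differs at Week 16.** The option to stay in the study off drug covers only Weeks 16 to 24. Protocol 8.2 sends other treatment discontinuers to Early Termination and follow-up visits. SAP 6.4 lets an early discontinuation visit be allocated to an analysis visit, so one on Days 100 to 127 could map to Week 16. The SAP does not say whether that counts as completing the Week 16 visit. A subject rescued before Week 16 while still on drug meets both definitions. The documents therefore do not show the two Week 16 sets differing in membership.

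**5. Imputation.** SAP 17.1.5 points to a section 16.1.3 that does not exist in the current numbering. Both candidates, 17.1.3 and 17.1.4, describe the rank ANCOVA combined over imputed datasets. SAP 17.1.3 uses 40 imputations with a separate model for each treatment group. In the planned-analyses table in SAP 17.2.1:

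- The DSQ completer cell carries footnote e, which states multiple imputation outright. The main DSQ analysis is a mixed model without it (footnote b).
- The completer cells for percent and absolute change in PEC carry footnote c, which mentions setting to missing but not imputation. The same footnote marks the primary ANCOVA and tipping-point cells for percent change, both of which use imputation, so it does not exclude it.
- The responder completer cells carry footnote d, which counts missing as nonresponse.

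So at Week 16 an attendee whose endpoint is missing, or set to missing after rescue, is filled in. A complete-case analysis would leave that subject out.

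**6. Size.** About 96 subjects at 3:3:2 gives 96 × 2/8 = 24 on placebo and 96 × 3/8 = 36 on each dose. One affected subject is 1/24 = 4.2% of the planned placebo arm or 1/36 = 2.8% of a planned dose arm. The documents give neither the number affected nor the number of completers.

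**The case against.** The strongest reply has four parts.

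First, the demonstrable difference in membership is at Week 24, while the primary and secondary endpoints are at Week 16. This stands. A reader might infer that off-drug, rescued subjects also fill the Week 16 set. The protocol's visit paths do not support that.

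Second, a reader might infer that every rescued attendee's PEC is imputed. Appendix 4 may instead keep PEC after off-drug rescue as observed, so that inference is too strong. The completers definition is unsatisfactory on either reading.

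Third, a result without imputation is already planned: SAP 17.1.6.2 runs an observed-data analysis in the mFAS. The Per Protocol Set (SAP 5.5) also comes close to a Week 16 completers set, since it excludes non-compliance, rescue that may affect the endpoint, and most missed Week 16 PEC. It would be wrong to say that the plan has no unimputed check. Still, the mFAS analysis does not require completed treatment. The Per Protocol Set keeps subjects whose Week 16 PEC is missing through discontinuation for lack of efficacy, and 17.1.5 repeats the primary model there too.

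Fourth, protocol 11.4.2 leaves detailed methods to the SAP. That covers how the analysis is run. It does not extend to replacing completed treatment by attendance, or complete-case by imputation, while declaring no change.

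**Conclusion.** The point holds as a minor one. SAP 5.9 and 17.1.5 together specify a different set and a different method from protocol 11.4.2, and SAP 3.3 does not say so. The difference in membership is documented for Week 24 only. At Week 16 the fault is the imputation. For DSQ the table states it. For PEC it is the natural reading of 17.1.5, which footnote c leaves unstated.

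The number of subjects affected cannot be derived. A reader might suppose two or three on placebo, which would be 2/24 = 8.3% to 3/24 = 12.5%. Nothing in the documents supports that count, and 24 is the planned number randomized to placebo, not the number of completers. The primary analysis is unaffected. What is at risk is the interpretation of a supplementary analysis.

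**What to change.** - **SAP 5.9:** define the Completers Sets as FAS subjects who completed 16 (or 24) weeks of study treatment and have a usable endpoint value at that visit. State whether an early termination visit allocated to Week 16 or Week 24 can qualify.
- **SAP 17.1.5 and the table footnotes in 17.2.1:** state that the completers analysis runs the rank ANCOVA for the primary endpoint, and the corresponding models for the secondary endpoints, without imputation. Correct the cross-reference to 16.1.3.
- **SAP Appendix 4 and 17.1.2:** reconcile the two on therapy begun after the last double-blind dose, and say which last dose is meant for subjects who continue into the extension.
- **Alternative:** if the visit-based, imputed version is intended, declare it in SAP 3.3 and drop the complete-case description.

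Protocol 11.4.2 does not require completers to be free of rescue. If the sponsor wants that condition, it should be stated as an addition and not attributed to the protocol.

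The cost is a few SAP sentences and no change to trial conduct. The set becomes slightly smaller and is selected on events after randomization, so its result should be read as supplementary only.

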5.10. EFFICACY EVALUABLE SET

The Efficacy Evaluable Set will be derived for the Extension Treatment Period only and includes all randomized subjects who receive at least 1 dose of study treatment and have at least one efficacy measurement in the Extension Treatment Period. Subjects will be analyzed according to treatment received in the Double-Blind Treatment Period and Extension Treatment Period (see treatments/treatment sequences in **Section 4.2** for more details).

Note that the Efficacy Evaluable Set can vary with endpoints since some subjects may have the needed data for inclusion in the Efficacy Evaluable Set for some endpoints, but not for other endpoints.

6. GENERAL CONSIDERATIONS

6.1. REFERENCE START DATE AND STUDY DAY

Study Day will be calculated from the reference start date and will be used to show start/stop day of assessments and events. Unless specified otherwise, reference start date is defined as the date of first dose (Day 1) and will appear in every listing where an assessment date or event date appears.

If the date of the event is on or after the reference date then:

$$\text{Study Day} = (\text{date of event} - \text{reference date}) + 1$$

If the date of the event is prior to the reference date then:

$$\text{Study Day} = (\text{date of event} - \text{reference date})$$

In the situation where the event date is partial or missing, Study Day, and any corresponding durations will appear missing in the listings.

6.2. BASELINE

Unless otherwise specified, Baseline for the Double-Blind Treatment Period is defined as the last non-missing measurement taken prior to the first dose (including unscheduled assessments), and Baseline for the Extension Treatment Period is defined as the last non-missing measurement taken prior to the date of first dose in Extension Treatment Period at Week 24. If measurements include time (except for Quality of Life assessments (QoL)), the date/time will be used to define Baseline. Otherwise, only dates will be compared. QoL baseline is measured on Day 1 prior to the first dose. In the case where the last non-missing measurement and the date of first dose coincide and time is not collected, if the measurement was planned in the protocol to be done prior to the date of first dose, that measurement will be considered in defining Baseline.

6.3. RETESTS, UNSCHEDULED VISITS, AND EARLY TERMINATION DATA

For by-visit analyses and summaries, efficacy, safety, health-related quality of life, and CCI (including scheduled, retests, unscheduled, and early termination) will be assigned to visits after the application of the windowing conventions described in Section 6.4. All measurements will be considered in summaries of abnormalities or worst-case values post-Baseline.

The visit windowing will be applied before missing data are imputed.

Listings will include scheduled, unscheduled, retest, and early discontinuation data.

6.4. WINDOWING CONVENTIONS

All scheduled study visits are defined relative to Study Day 1, the date of first dose. Scheduled visit windows are defined in Appendix 1 of the protocol. A windowing convention will be used to determine the analysis visit value for a given measurement and will be applicable for all by-visit summaries and analyses for efficacy and safety data. See Table 3 below for specific visit windows.

Visit Windows for Efficacy and Safety Analyses

For all efficacy (except for DSQ total score), CCI health-related quality of life, safety labs and vital signs.	
Scheduled Study Visit (Protocol Scheduled Day)	Analysis Visit Window (Study Day)
Baseline (Double-Blind Treatment Period)	≤ 1 , in addition to Study Day ≤ 1 , a measurement also needs to fulfill the baseline criteria identified in Section 6.2 in order to be considered as baseline measurement
Week 0 (Day 1)	1
Week 2 (Day 15 \pm 3)	2 to 22
Week 4 (Day 29 \pm 3)	23 to 43
Week 8 (Day 57 \pm 5)	44 to 71
Week 12 (Day 85 \pm 5)	72 to 99
Week 16 (Day 113 \pm 5)	100 to 127
Week 20 (Day 141 \pm 5)	128 to 155
Week 24 (Day 169 \pm 5)	156 to 183
Week 28 (Day 197 \pm 7)	184 to 211
Week 32 (Day 225 \pm 7)	212 to 274
Week 46 (Day 323 \pm 7)	275 to 344
Week 52 (Day 365 \pm 7)	> 344

DSQ total score will be calculated every 2 weeks (week 0, 2, 4, 6, 8, 10, etc.) based on the scheduled study day starting on Day 1 For example, DSQ total score for Week 2, 4 and 6 will be calculated on Day 15, 29 and 43, respectively. .

For ECGs, OCT, and PFT.

Scheduled Study Visit (Protocol Scheduled Day)	Analysis Visit Window (Study Day)
Baseline (Double-Blind Treatment Period)	≤ 1
Week 0 (Day 1)	1
Week 24 (Day 169 ± 5)	71 to 267
Week 52 (Day 365 ± 7)	> 267

Windowing will be applied prior to any missing data calculations. The measurement that meets the Baseline criteria described in Section 6.2 will be labeled as “Baseline”. Unscheduled or Screening visits that occurred before the Baseline visit will not be assigned an analysis visit. The early discontinuation visit will be eligible for allocation to an analysis visit. The 2- and 4-Week Follow-Up visits will not be included in the visit windows and will be summarized separately without any window applied.

If one or more results for a variable are assigned to the same analysis visit, the result with the date closest to the protocol scheduled day will be used in the analysis. If two measurements in the same analysis visit window are equidistant from the protocol scheduled study day, the earlier measurement will be used in the analysis. If multiple assessments are available on the same day, then the average of the assessment will be used in the analysis, except for laboratory and ECG data where the assessment at the earliest time of the same day will be used. If both central and local assessments of the same lab test are available on the same day, the central result will take precedence over the local result. If both central and local assessments of the same ECG test are available on the same day, the assessment of clinical significance by local reader will take precedence over the determination by a central reader.

